13.1.3 Faecal Sampling

Faecal samples will be collected according to the time schedule presented in [Appendix 2](#).

The pre-dose faecal sample will be taken from admission until pre-dose. If a pre-dose faecal sample cannot be obtained, the subject will still be dosed. Where a sample is not provided, this will not be considered a deviation.

Samples and toilet paper will be collected into appropriate pots/containers as specified by the metabolism laboratory. Details of sample containers and processing will be contained in the Clinical Sample Processing Manual.

Samples will be shipped to Pharmaron for the analysis of total radioactivity and for metabolite profiling and identification.

13.1.4 Unexpected Sources of Elimination

During the study, other accidental sources of elimination will be collected as voided (eg emesis).

Samples will be shipped to Pharmaron for the analysis of total radioactivity.

13.2 Assessment of Pharmacodynamics

Not applicable for this Phase I study.

14 Assessment of Safety

14.1 Definition and Classification of Adverse Events

An AE is any untoward medical occurrence in a subject that occurs either before dosing (referred to as a pre-dose AE) or once a medicinal product has been administered, including occurrences which are not necessarily caused by or related to that product.

An adverse drug reaction is any AE where a causal relationship with the IMP is at least a reasonable possibility (possibly related or related).

AEs will be monitored from the time the subject signs the ICF until discharge from the study. The severity of AEs should be assessed as follows:

- | | |
|-----------------|--|
| Mild | An AE that is easily tolerated by the subject, causes minimal discomfort and does not interfere with everyday activities |
| Moderate | An AE that is sufficiently discomforting to interfere with normal everyday activities; intervention may be needed |
| Severe | An AE that prevents normal everyday activities; treatment or other intervention usually needed |

14.2 Assessment of Causality

Every effort should be made by the investigator to try to explain each AE and assess its relationship, if any, to the IMP. The temporal relationship of the event to IMP administration should be considered in the causality assessment (ie if the event starts soon after IMP administration and resolves when the IMP is stopped).

Causality should be assessed using the following categories:

Unrelated: Clinical event with an incompatible time relationship to IMP administration, and that could be explained by underlying disease or other drugs or chemicals or is incontrovertibly not related to the IMP

Possibly related: Clinical event with a reasonable time relationship to IMP administration, and that is unlikely to be attributed to concurrent disease or other drugs or chemicals

Related: Clinical event with plausible time relationship to IMP administration and that cannot be explained by concurrent disease or other drugs or chemicals

The degree of certainty with which an AE is attributed to IMP administration (or alternative causes, eg natural history of the underlying disease, concomitant therapy) will be determined by how well the experience can be understood in terms of one or more of the following:

- known pharmacology of the IMP
- reactions of a similar nature have been previously observed with the IMP or this class of drug
- the experience being related by time to IMP administration, terminating with IMP withdrawal or recurring on re-challenge
- alternative cause

14.3 Recording Adverse Events

AEs will be recorded from the time of providing written informed consent until discharge from the study. During each study visit the subject will be questioned directly regarding the occurrence of any adverse medical event according to the schedule in the source. All AEs, whether ascribed to study procedures or not, will be documented immediately in the source. This will include the date and time of onset, a description of the AE, severity, duration, actions taken, outcome and an investigator's current opinion on the relationship between the study drug and the event. A diagnosis and final opinion on the relationship between the study drug and the event will be provided at the end of the study by the investigator.

Any subject who withdraws from the study due to an AE will be followed up until the outcome is determined and written reports provided by the investigator.

14.4 Serious Adverse Events

14.4.1 Definition of Serious Adverse Events

A serious adverse event (SAE) is defined as any untoward medical occurrence that at any dose:

- results in death
- is life-threatening
- requires hospitalisation or prolongation of existing hospitalisation
- results in persistent or significant disability or incapacity
- consists of a congenital anomaly or birth defect
- an important medical event as recognised by the PI

SAEs must be immediately (without any delay) reported to the sponsor and in any case no later than 24 h of becoming aware of the event.

14.4.2 Definition of Suspected Unexpected Serious Adverse Reactions

Suspected unexpected serious adverse reactions (SUSARs) are AEs that are believed to be related to an IMP and are both unexpected (ie the nature or severity is not expected from the information provided in the Reference Safety Information (RSI) section of the Investigator's Brochure Edition No 10) and serious. SUSARs are subject to expedited reporting to the MHRA, European Medicines Agency (EMA) and EC (see [Section 16.3.2](#) for details on reporting SUSARs).

14.5 Laboratory Measurements

Venous blood, urine and faecal samples will be collected from the subjects by a trained member of the clinical team. Consent will be collected from the subjects for use of these samples for the purposes of the proposed study.

Blood, urine and faecal samples are sent for laboratory testing in linked anonymised form (subject number, initials and the subjects' gender and date of birth for analytical reasons). This information is able to be linked directly to the volunteer by the Quotient research team and study monitor, however not by the laboratory staff or sponsor.

Safety laboratory tests and virology will be carried out on blood samples, and drugs of abuse tests and urinalysis will be carried out on urine samples. The research will not involve analysis or use of human DNA.

Blood and urine samples results will be reviewed by a physician and acted upon before the subject is dosed or receives their next dose, or is released from the study, as is appropriate. A list of the laboratory parameters measured is presented in [Appendix 1](#).

14.5.1 Haematology and Clinical Chemistry

Laboratory tests will be performed by The Doctors Laboratory according to the time schedule presented in [Appendix 2](#). Blood samples will be collected and processed as detailed in the Clinical Sample Processing Manual. Scheduled blood samples will be taken following an 8 h fast.

The acceptable deviations from the nominal blood sampling time points for laboratory assessments are:

- The pre-dose blood sample will be taken ≤ 2 h before dosing
- Post-dose blood samples will be taken ± 1 h from the nominal blood sampling time

Creatinine clearance (CLcr) will be calculated at screening by The Doctors Laboratory using the Cockcroft-Gault equation and body weight for eligibility purposes:

$$\text{CLcr (mL/min)} = \frac{(140 - \text{age [years]}) \times (\text{body weight [kg]}) \times 1.23}{\text{serum creatinine } (\mu\text{mol/L})}$$

14.5.2 Urinalysis

Urinalysis will be performed on-site using a dipstick according to the time schedule presented in [Appendix 2](#). Urine samples will be collected and processed as detailed in the Clinical Sample Processing Manual. If microscopy is required, a urine sample will be sent to The Doctors Laboratory. Any urine used for urinalysis will be added back to the full sample for total radioactivity analysis. If microscopy is required, a urine sample (approximately 20 mL) will be taken from the urine collection, and sent to The Doctors Laboratory after the void has been weighed.

The acceptable deviations from the nominal urine sampling time points for urinalysis are:

- The pre-dose urine sample will be taken ≤ 3 h before dosing or the first void of the day
- Post-dose urine samples will be taken ± 2 h from the nominal urine sampling time

14.5.3 Drug Screen

A urine drug screen will be performed on-site using a dipstick method according to the time schedule presented in [Appendix 2](#). The sample will be collected and processed as detailed in the Clinical Sample Processing Manual. Subjects will be screened for the drugs of abuse listed in [Appendix 1](#).

14.5.4 Alcohol Breath Test

An alcohol breath test will be performed according to the time schedule presented in [Appendix 2](#). A positive result will exclude the subject from dosing during that admission.

14.5.5 Carbon Monoxide Breath Test

A carbon monoxide breath test will be performed according to the time schedule presented in [Appendix 2](#). A result of greater than 10 ppm will exclude the subject from the study.

14.5.6 Abnormal Laboratory Findings

In cases where laboratory findings are outside the normal range and the investigator believes that the results may be of clinical significance, repeat sampling may be requested as clinically indicated. If the abnormal finding is clinically significant, appropriate actions will be taken eg the subject will not be entered into the study or the subject may be withdrawn from the study. The subject will be referred to their GP or other appropriate provider for further care. The same will apply if the results of the HBsAg, HCV Ab or HIV test are positive and in addition the investigator will ensure that adequate counselling is available if requested.

Abnormal results at follow-up assessments will also require repeat testing if the investigator believes the results may be of clinical significance.

Any clinically significant abnormality, including changes from baseline, must be reported as an AE.

Additional blood and/or urine samples may be taken for safety tests. Furthermore, additional assays outside those specified in the protocol may be performed for safety reasons as requested by the investigator or sub-investigator.

14.6 Vital Signs Measurements

Blood pressure and heart rate will be measured by an automated recorder after the subject has been in a supine position for a minimum of 5 min according to the time schedule presented in [Appendix 2](#). Oral temperature will also be measured. The acceptable deviations from the nominal vital signs measurement time points are:

- The pre-dose vital signs measurements will be taken ≤ 2 h before dosing.
- Post-dose vital signs measurements will be taken ± 15 min from the nominal post-dose time points.
- Discharge vital signs measurements will be taken ± 1 h from the nominal time point.

If a subject shows an abnormal assessment at any stage, repeat measurements may be made and the abnormality followed to resolution if required. Additional measurements may be taken as deemed necessary by the investigator or sub-investigator.

Any clinically significant abnormality, including changes from baseline, must be reported as an AE.

14.7 ECG Measurements

Single 12-lead ECGs will be measured after the subject has been in the supine position for a minimum of 5 min according to the time schedule presented in [Appendix 2](#). The acceptable deviations from the nominal ECG measurement time points are:

- The pre-dose ECG measurements will be taken ≤ 2 h before dosing
- Post-dose ECG measurements will be taken ± 15 min from the nominal post-dose time point.
- Discharge ECG measurements will be taken ± 1 h from the nominal time point.

If a subject shows an abnormal assessment at any stage, repeat measurements may be made and the abnormality followed to resolution if required. Additional measurements may be taken as deemed necessary by the investigator or sub-investigator.

Any clinically significant abnormality, including changes from baseline, will be reported as an AE.

14.8 Body Weight and Height

The subject's body weight and height will be measured as detailed in [Appendix 2](#).

14.9 Physical Examination

Subjects will undergo a physical examination as detailed in [Appendix 2](#).

14.10 Additional Safety Procedures

Additional non-invasive procedures that are already specified in the protocol may be performed, if it is believed that an important effect of the IMP(s) is occurring or may occur at a time when no measurements are scheduled, or if extra procedures are needed in the interests of safety.

Additional blood samples for safety assessments may be taken if required by the investigator at any point.

15 Statistics and Data Analysis

15.1 Sample Size Justification

The study is exploratory and no formal sample size calculation has been made. Based on experience from previous studies of a similar design, a total of 6 subjects is to be enrolled and a minimum of 4 evaluable subjects is considered sufficient.

15.2 Data Management

Data management will be performed by Quotient Sciences.

Study data will be managed using a validated electronic case report form (eCRF) database system and subjected to data consistency and validation checks. Data queries will be raised within the study eCRF database by data management staff and resolved with the assistance of clinical staff.

AEs and medications will be coded using the Medical Dictionary for Regulatory Activities (MedDRA) (v22.0 or a more recent version) and the World Health Organisation (WHO) Drug Dictionary Global Drug Reference (2019 or a more recent version), respectively. An independent coding review will also be performed within the Data Sciences department.

Clinical chemistry and haematology data (and other safety laboratory data) will be collected by a central laboratory (The Doctors Laboratory) and stored electronically in their clinical pathology system. The data will be transferred electronically to Quotient Sciences and all demographic details and sample dates will be cross-referenced with the corresponding data on the study database. All queries will be resolved with the assistance of laboratory staff, or if necessary, clinical staff.

The database will be closed after all queries have been resolved. The database will be locked when all criteria listed in the Data Management Plan (DMP) are met.

Further details are addressed in the DMP.

15.3 Mass Balance Data Analysis

Urine and faeces will be collected for the analysis of total radioactivity. Graphical and tabular representation of whole blood and plasma total radioactivity concentrations and ratios at selected time points will be presented. The following mass balance parameters will be calculated by Quotient Sciences for urine, faeces and combined urine and faeces (ie total radioactivity from all excreta).

| Parameter | Definition |
|------------------|---|
| Ae(urine) | Amount of total radioactivity excreted in urine |
| %Ae(urine) | Amount of total radioactivity excreted in urine expressed as a percentage of the radioactive dose administered |
| CumAe(urine) | Cumulative amount of total radioactivity excreted in urine |
| Cum%Ae(urine) | Cumulative amount of total radioactivity excreted in urine expressed as a percentage of the radioactive dose administered |
| Ae(faeces) | Amount of total radioactivity eliminated in faeces |
| %Ae(faeces) | Amount of total radioactivity eliminated in faeces expressed as a percentage of the radioactive dose administered |
| CumAe(faeces) | Cumulative amount of total radioactivity eliminated in faeces |
| Cum%Ae(faeces) | Cumulative amount of total radioactivity eliminated in faeces expressed as a percentage of the radioactive dose administered |
| Ae(total) | Amount of total radioactivity excreted in urine and faeces combined |
| %Ae(total) | Amount of total radioactivity excreted in urine and faeces combined expressed as a percentage of the radioactive dose administered |
| CumAe(total) | Cumulative amount of total radioactivity excreted in urine and faeces combined |
| Cum%Ae(total) | Cumulative amount of total radioactivity excreted in urine and faeces combined expressed as a percentage of the radioactive dose administered |

15.4 Pharmacokinetic Data Analysis

The plasma concentration data for MD1003, bisnorbiotin and biotin sulfoxide, and plasma and whole blood total radioactivity concentrations provided by Pharmaron will be analysed by Quotient Sciences using Phoenix WinNonlin v8.0 or a more recent version (Certara USA, Inc., USA).

Calculated MD1003 concentrations may be corrected for specific activity of the administered radiolabelled oral dose by the Data Sciences department at Quotient Sciences.

Plasma concentration data will be tabulated and plotted for each subject for whom concentrations are quantifiable. PK analysis of the concentration time data obtained will be performed using appropriate non-compartmental techniques to obtain estimates of the following PK parameters:

| Parameter | Definition |
|-----------------------|---|
| Tlag | Time prior to the first measurable (non-zero) concentration |
| Tmax | Time of maximum observed concentration |
| Cmax | Maximum observed concentration |
| AUC(0-last) | Area under the curve from 0 time to the last measurable concentration |
| AUC(0-inf) | Area under the curve from 0 time extrapolated to infinity |
| AUCextrap | Percentage of AUC(0-inf) extrapolated beyond the last measurable concentration |
| T1/2 | Apparent elimination half-life |
| Lambda-z | Slope of the apparent elimination phase |
| CL/F (MD1003 only) | Apparent total body clearance calculated after a single extravascular administration where F (fraction of dose bioavailable) is unknown |
| Vz/F (MD1003 only) | Apparent volume of distribution based on the terminal phase calculated after a single extravascular administration where F (fraction of dose absorbed) is unknown |
| MPR Cmax | Metabolite to parent ratio based on Cmax |
| MPR AUC(0-inf) | Metabolite to parent ratio based on AUC(0-inf) |

Further details of the PK data analysis will be included in the Reporting and Analysis Plan (RAP).

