5.1 Introduction

MD1003 is the code name for high doses of pharmaceutical-grade biotin being developed by MedDay Pharmaceuticals as a treatment for patients with primary and secondary progressive multiple sclerosis (MS).

MD1003 is a powder of biotin in hard capsule (100 mg per capsule). The therapeutic dose of MD1003 is 300 mg/day (ie between 3 and 6 mg/kg/day) [1].

Biotin is a water-soluble vitamin acting as a carboxyl (CO₂) transporter in carboxylation reactions. In mammals, biotin serves as a cofactor for four carboxylases involved in the metabolism of carbohydrates, amino acids and fatty acids: (1) pyruvate carboxylase (PC), (2) 3-methylcrotonyl-CoA carboxylase (MCC), (3) propionyl-CoA carboxylase (PCC) and (4) acetyl-CoA carboxylase (ACC) [2]. These carboxylases play a critical role in the intermediate metabolism of gluconeogenesis, fatty acid synthesis, and amino acid catabolism

Of note, in the nervous system, ACC1 and ACC2 are detected exclusively in oligodendrocytes, the cells responsible for myelin synthesis, and are found in purified myelin, suggesting that these enzymes are key regulators of myelin synthesis [3].

Besides its role as a co-factor, biotin may regulate genes encoding enzymes or transporters involved in its own metabolism or other cell function [4]. However, this physiological role of biotin remains unclear.

MD1003 is expected to be the first therapeutic approach having an impact on not active progressive MS by reversing the “virtual hypoxia” phenomenon and triggering remyelination [5],[6].

It was hypothesised that the positive effects of MD1003 that are seen in demyelinating diseases such as multiple sclerosis are linked to: (1) increased energy production through feeding the tricarboxylic acid (TCA) cycle in demyelinated neurons and in oligodendrocytes, and (2) stimulation of myelin repair through activation of the acetyl-CoA carboxylase in oligodendrocytes [6].

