5.3.1 Non-clinical Findings

The hypothesised positive effects of MD1003 that may be seen in demyelinating or dysmyelinating diseases such as MS are thought to be linked to: (1) increased energy production through augmenting the TCA cycle in demyelinated neurons, and (2) stimulation of myelin repair through activation of the acetyl-CoA carboxylase in oligodendrocytes.

Following oral administration, biotin is absorbed in the intestine via the sodium multivitamin transporter (SMVT). At the therapeutic dose level, biotin has good oral bioavailability (~50%) and is largely not bound to plasma proteins. Following an oral administration of MD1003 in rats, the highest concentrations were found in the stomach, bladder, and kidneys with a rapid elimination with very low concentrations after 24 h and no storage of biotin observed. Biotin uptake into the CNS, liver, and most peripheral tissues also involves the SMVT. No saturation of the SMVT at the blood-brain barrier is expected at the therapeutic dose. Biotin may accumulate in the placenta and is excreted in milk in animals. Biotin is catabolized mostly in the liver via 2 pathways leading to 2 main metabolites, bisnorbiotin and biotin sulfoxide. Biotin metabolites are inactive. Following an intravenous administration of MD1003 in rats, biotin and its metabolites are rapidly excreted in the urine (>80% of elimination) with biotin being the major form excreted. Urinary clearance data obtained following administration of MD1003 in healthy volunteers suggest that biotin is actively secreted by the kidneys.

Drug interaction with MD1003 treatment involving cytochrome P450 enzymes or transporters commonly involved in the absorption, metabolism and elimination of other drugs are not expected. The expected risk of drug interaction with MD1003 administration in humans resides mainly from pharmacodynamic interaction with insulin and pharmacokinetic (PK) interactions with other substrates of the biotin transporter (SMVT) and some antiepileptic drugs (carbamazepine, oxcarbazepine, primidone, and valproate semisodium).

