5.3.4 Pharmacokinetics and Product Metabolism in Animals

Full details of PK and absorption, metabolism, distribution and elimination (ADME) data can be found in the Investigator's Brochure [1].

In the GLP Study MD1003-ADME-RAT, the radioactivity was rapidly eliminated from plasma after intravenous administration of 10 mg/kg ¹⁴C-MD1003. After oral administration of 30 mg/kg ¹⁴C-MD1003 (human equivalent therapeutic dose), the radioactivity was rapidly absorbed and after a first phase of rapid elimination from the plasma, the radioactivity was then slowly eliminated.

At physiological doses of [¹⁴C] biotin (88 nmol/kg body weight) given orally to pigs, the plasma concentration profile best fitted a tri-exponential equation [9], which corresponds to a tricompartamental open model. Disappearance curves of total ¹⁴C and of [¹⁴C] biotin were similar. Biotin pharmacokinetics after intravenous injection of [¹⁴C] biotin was marked by a very short half-life of the initial distribution phase (7 min), followed by a slower plasma elimination phase (T_{1/2}, β of 1.43 h) and a long apparent terminal half-life T_{1/2}, γ estimated at 22 h. The rapid initial distribution phase was shown to correspond to the disappearance of biotin from the plasma (central compartment) to the peripheral compartments, such as the total body water pool or tissue pools [9].

The retention over many days of a substantial portion of the administered dose may occur as a consequence of the metabolic trapping of biotin into cells: conversion of biotin to intermediates such as biotinyl-adenosine monophosphate and biotinyl-CoA, or binding of biotin to proteins such as carboxylases and histones [9]. The half-life of pyruvate carboxylase was determined to be 28 h and 4.6 days for acetyl-CoA carboxylase [10].

Overall, PK data obtained with MD1003 confirmed the literature data and completed the PK properties of biotin:

- Biotin is rapidly absorbed by the oral route in animals

- At the equivalent therapeutic dose in rats (30 mg/kg), biotin is not completely absorbed
- At very high doses (up to 3000 mg/kg), plasma exposure does not significantly increase, suggesting that the transport is saturated
- The major route of elimination is urinary and most of the biotin is excreted unchanged
- There was no evidence of accumulation after once daily repeated dosing in animals

6 Rationale

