19. Donation or loss of greater than 400 mL of blood within the previous 3 months
20. Subjects who are taking, or have taken, any prescribed or over-the-counter drug (other than 4 g of paracetamol per day), herbal remedies, vitamin B5 or dietary supplements containing lipoic acid in the 14 days before IMP administration (see [Section 11.4](#)). Exceptions may apply on a case by case basis, if considered not to interfere with the objectives of the study, as determined by the PI
21. Subjects who have had any intake of biotin (including as a nutritional supplement) in the 14 days before IMP administration
22. Failure to satisfy the investigator of fitness to participate for any other reason

Exclusion criteria [6](#), [7](#), [9](#), [10](#), [12](#), [13](#), [18](#), [19](#), [20](#), [21](#) and [22](#) from the list above will be re-assessed at admission/pre-dose.

Healthy subjects who do not meet the inclusion/exclusion criteria for the study will not be enrolled.

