13.1 Assessment of Mass Balance, Pharmacokinetics and Metabolite Profiling and Identification

13.1.1 Blood Sampling

Venous blood samples will be collected from the subjects by a trained member of the clinical team. Consent will be collected from the subjects for use of these samples for the purposes of the proposed study.

Plasma and whole blood samples are sent for laboratory testing in linked anonymised form (subject number only). This information is able to be linked directly to the volunteer by the Quotient research team and study monitor, however not by the laboratory staff or Sponsor.

Venous blood samples will be withdrawn via an indwelling cannula or by venepuncture according to the time schedule presented in [Appendix 2](#).

The acceptable deviations from the nominal blood sampling times are as follows:

- The pre-dose samples will be taken ≤ 1 h before dosing
- 0 to 1 h post-dose samples will be taken within ± 2 min of the nominal post-dose sampling time
- >1 to 12 h post-dose samples will be taken within ± 10 min of the nominal post-dose sampling time
- >12 h post-dose samples will be taken within ± 30 min of the nominal post-dose sampling time

Samples will be collected into appropriate tubes as specified by the bioanalytical laboratory. Details of sample tubes and processing will be contained in the Clinical Sample Processing Manual.

Samples will be shipped to Pharmaron for the analysis of total radioactivity in plasma and whole blood, and for metabolite profiling and identification in plasma. Samples will be shipped to Atlanbio for the analysis of MD1003, bisnorbiotin and biotin sulfoxide in plasma.

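### Do the Tlag, AUC(0-last) and AUCextrap definitions go wrong for biotin because they ignore the pre-dose level?

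*Protocol*

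**What the plan says.** Section 15.4 (repeated in the Synopsis, Section 3) lists the parameters to be obtained by non-compartmental analysis. Three are worded in terms of what can be measured:

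- Tlag: "Time prior to the first measurable (non-zero) concentration"
- AUC(0-last): "Area under the curve from 0 time to the last measurable concentration"
- AUCextrap: "Percentage of AUC(0-inf) extrapolated beyond the last measurable concentration"

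Lambda-z is described only as the slope of the apparent elimination phase. The section allows MD1003 concentrations to be corrected for the specific activity of the dose before analysis, calls for individual concentration plots, and leaves further detail to the RAP. Section 15.6 requires the RAP to be signed off before database lock.

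On the analyte, Section 5.1 says that "biotin serves as a cofactor for four carboxylases", and Section 5.3.1 that "Biotin is catabolized mostly in the liver via 2 pathways leading to 2 main metabolites, bisnorbiotin and biotin sulfoxide". Section 13.1.1 provides for a pre-dose blood sample and sends samples "for the analysis of MD1003, bisnorbiotin and biotin sulfoxide in plasma", separately from the radioactivity assay. Section 9.3 excludes subjects with "any intake of biotin (including as a nutritional supplement) in the 14 days before IMP administration".

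**The concern.** Read literally, the definitions suit a compound that is absent before dosing. Biotin is a vitamin, the two metabolites are its own breakdown products, and all three are assayed by concentration, not by label. The 14-day exclusion shows that the protocol takes earlier biotin intake seriously. Yet the pre-dose sample enters no definition, and the only correction named is for specific activity.

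If the pre-dose sample were quantifiable and nothing were done about it, two things would follow. The first non-zero concentration would be the pre-dose one, so Tlag would be 0 for everyone. Late samples sitting at the background level would also count as measurable and could enter the terminal fit. T1/2 and AUC(0-inf) would then be too high, CL/F too low and Vz/F too high, and the metabolite-to-parent AUC ratio would shift in an unknown direction. Section 5.3.4 reports "a long apparent terminal half-life" in pigs and possible retention over many days, so the terminal phase is a real question for this compound.

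**Working it through.** The protocol states no figure on this point, so there is none to reproduce. Two checks apply: how large the effect is if it occurs, and whether the text commits the analysis to it.

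**Size, if triggered.** None of these inputs comes from the protocol:

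- one-compartment oral curve scaled to Cmax = 1
- absorption rate 2/h, lag 0.3 h
- constant baseline B as a fraction of Cmax
- assay limit 0.01% of Cmax
- Lambda-z from the last three measurable points.

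Take a true half-life of 8 h and last samples at 24, 36 and 48 h. The drug-derived concentrations are 0.1546, 0.0547 and 0.0193 of Cmax. For three equally spaced points the log-linear slope is ln(C24/C48)/24.

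- B = 0: ln(0.1546/0.0193)/24 = ln(8)/24 = 0.0866 per h, so T1/2 = 0.693/0.0866 = 8.00 h.
- B = 1%: ln(0.1646/0.0293)/24 = 0.0719 per h, so T1/2 = 9.64 h.
- B subtracted: the first line returns, T1/2 = 8.00 h.

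Other cases from the same model:

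| Last sample | True T1/2 | B = 0.1% | B = 1% | B = 5% |
|---|---|---|---|---|
| 24 h | 22 h | 22.0 h | 22.4 h | 23.8 h |
| 48 h | 8 h | 8.17 h | 9.64 h | 15.4 h |
| 168 h | 22 h | 24.0 h | 40.8 h | 110 h |

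For the 48 h row, AUC(0-last) rises from 13.055 to 13.105, 13.557 and 15.529, that is by 0.4%, 3.8% and 19%. AUCextrap goes from 1.7% to 1.8%, 2.9% and 9.0%. If sampling runs far past washout (true half-life 1.43 h, 168 h), the last points equal B and no slope can be estimated.

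Tlag is 0.25 h without a baseline and 0 with one. If there is no true lag, it is 0 either way.

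So the mechanism is correct, and its size runs from nothing to severe depending on B/Cmax and on sampling length relative to half-life.

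**Are those inputs in the document?** No pre-dose level, assay limit or Cmax is given. The blood sampling times belong to the Appendix 2 flow chart, whose table is not legible in the text at hand. Section 8.4 judges evaluability on samples up to 72 h. Section 8.1 stops blood collection at discharge or at the end of a residency of up to 168 h. The half-lives in Section 5.3.4 (1.43 h and 22 h) come from intravenous dosing in pigs.

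**Does the text commit the analysis to unadjusted data?** Section 15.4 defines what is computed from a concentration-time curve. It does not say that the curve is unadjusted. Pre-dose subtraction is a data step before non-compartmental analysis. Once it is done, the pre-dose value is zero and the first non-zero concentration has its ordinary meaning. The specific-activity correction shows that the section already foresees adjusting concentrations beforehand. A plateau at the pre-dose level is not an elimination phase, so the Lambda-z description does not oblige anyone to fit it.

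**The case for a change.** The strongest reply is that this is not a complaint about missing detail: the definitions are already written, in two places, and applied literally they mislead. The RAP should not be the only place where a protocol definition is put right. A two-phase simulation (the pig half-lives, 5-20% of AUC in the slow phase, baseline 0.1% of Cmax) makes the stakes concrete. With 72 h sampling, T1/2 comes out at 27-45 h against 22 h and AUC(0-inf) rises by 3% to 5%. With 168 h sampling, T1/2 is 99-369 h and AUC(0-inf) is up 8% to 21%, while AUCextrap is only 4-13% and would raise no alarm. Even after subtraction, a trivial positive residual would count as non-zero.

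Some of this stands. The arithmetic is right, a baseline is plausible, and the handling should be settled before the data are seen. But a RAP that specifies adjusted concentrations does not contradict Section 15.4; it supplies the input that the section leaves open. A margin for small residuals depends on assay precision, which is the RAP's business.

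The large figures rest on assumed baselines, slow-phase shares and sampling grids, and on noise-free data. In the 369 h case, adding an assumed 5-10% assay noise brings the median T1/2 to about 84-94 h and the AUC(0-inf) excess to about 10%. Bias remains, but the upper ends are overstated. At a baseline of 0.01% of Cmax, AUC(0-inf) moves by less than 1%.

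**Conclusion.** The concern does not hold. Section 15.4 gives ordinary definitions and is silent on baseline adjustment; it neither misstates a rule nor rules the adjustment out. That silence concerns a step commonly left to the analysis plan, and the protocol refers further pharmacokinetic detail to a RAP signed off before database lock. Whether pre-dose biotin is quantifiable, and whether it matters beside a 100 mg dose, cannot be told from the document, so the effect cannot be sized beyond the range from nil to material.

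What could be affected is limited to secondary parameters of MD1003, bisnorbiotin and biotin sulfoxide, summarised descriptively in about six subjects without any hypothesis test. Mass balance and all total-radioactivity parameters follow the carbon-14 label and are unaffected. A reader with the RAP may reasonably look there for how pre-dose concentrations are handled. The conclusion rests on reading the definitions as applying to whatever concentrations the RAP specifies; it would change if the RAP fixed unadjusted concentrations despite quantifiable pre-dose values.
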